A MOBILE HEALTH INTERVENTION TO INCREASE UPTAKE OF PRENATAL CARE IN SYRIAN REFUGEE POPULATION IN TURKEY

Study Protocol and Statistical Analysis Plan (SAP)

Protocol Identification Number: HeraInc

Clinicaltrials.gov identifier: XXXXXXXX

09/02/2021

STATISTICAL ANALYSIS PLAN (SAP)

A MOBILE HEALTH INTERVENTION TO INCREASE UPTAKE OF PRENATAL CARE IN SYRIAN REFUGEE POPULATION IN TURKEY

Principal Investigator

[name], PhD

Assistant Professor of Public Health

Acibadem Mehmet Ali Aydinlar University

School of Medicine

Department of Medical Sciences

Istanbul, Turkey

Protocol Identification Number

HeraInc

Clinicaltrials.gov Identifier

XXXXXX

Author

[name], MA

Public Health

Harvard T. H. Chan School of Public Health

Massachusetts, USA

Senior Statistician

[name]

SAP Version and date

0.1 (08/31/2021)

SAP Reviewers

[name]

1. Signature page

Principal Investigator

Senior Statistician

Author

2. Abbreviations

WHO	World Health Organization
MoH	Ministry of Health
HERA	Health Recording Application

3. Table of contents

1. Signature page	2
2. Abbreviations	3
3. Table of contents	4
4. Modification history	5
5. Introduction	5
5.1. Background and Rationale of the Study	5
5.2. Objectives	6
5.3. Hypotheses	6
6. Study methods	6
6.1. Study Type	6
6.2. Study Procedure	7
6.2.1. Recruitment Strategy	8
6.3. Study Population	8
6.3.1. Eligibility	8
6.4. Sample Size Determination	9
6.5. Randomization Strategy	9
7. Outcomes	10
7.1. Populations and subgroups to be analyzed Per Protocol (PP)	10
8. Analysis..	11
8.1. Primary Outcome	11
8.2. Secondary Outcomes	11
8.3. Missing Data	11
8.4. Timing of the Final Analysis	11

4. Modification History

Unique Identifier for SAP Version	Date of SAP Version	Authors	Changes From the Previous Version
Draft V0.1	08/31/2021	[name]	Not applicable – first version

5. Introduction

The purpose of this study is to assess the effectiveness of mobile phone-based appointment reminder notifications sent through the HERA app in increasing the uptake of 4 WHO recommended prenatal visits among the Syrian refugee population.

The purpose of this Statistical Analysis Plan (SAP) is to document technical and detailed specifications for the final analysis of the data collected from protocol XXXXXX.

5.1. Background and Rationale of the Study

According to the UN, The Syrian refugee crisis is the worst humanitarian crisis since World War 2^[1]. Since the start of the Syrian Civil War in 2011, 12 million Syrians have been forcibly displaced from their homes. Turkey hosts nearly 4 million of these refugees, which constitutes the largest population of refugees in the world.^[2] Healthcare services are free in Turkey for the Syrian refugee population through national insurance; however, demand-side barriers such as language, not knowing where to receive care, and fear of deportation persist. Pregnant Syrian women are especially vulnerable to barriers to care. Peer-reviewed studies in Turkish hospitals indicate that refugee women are more likely to die during and after labor^[3]; additionally, less than 50% of pregnant Syrians attend at least four prenatal care visits^[4].

A robust body of research evidence supports the use of mobile phone-based reminder platforms to increase timely, complete access to health services. Mobile phone-based reminders have been shown in randomized controlled trials and systematic reviews to increase the uptake of various

services, including prenatal care.^{[5][6]} A systematic review found that the majority of text message reminder interventions improved health outcomes.^[7] Mobile phone penetration is high among Syrian refugees in Turkey^[8] and qualitative studies demonstrate that mobile health interventions are acceptable and feasible for Syrian refugees.^[9]

5. 2. Objectives

The primary objective of this study is to evaluate the impact of mobile phone-based reminders on the uptake of prenatal care among pregnant Syrian refugee women. More specifically, the study assesses the effectiveness of mobile phone-based reminders by measuring the percent increase in the number of prenatal appointments attended by intervention arm participants compared to the control arm participants.

5. 3. Hypotheses

Null hypothesis: Sending reminders on participants' upcoming appointments 2 weeks before, 1 day before, and on the day of the appointment will not have any effect on the number of appointments that are attended. Thus, the mean number of visits will not vary significantly across the 3 arms.

Alternative hypothesis: Sending reminders on participants' upcoming appointments 2 weeks before, 1 day before, and on the day of the appointment will result in a percent increase on the number of appointments that are attended by the intervention group compared to the control groups.

6. Study Methods

6. 1. Study Type

This is a behavioral intervention study using an unblinded, parallel groups, randomized controlled study design. The intervention group ("Reminder") will download and use the HERA application to receive appointment reminders through push notifications. The control group ("No reminder") will not be using the HERA application, and therefore won't be provided with any reminders. The third group will also be a non-notified control group, i.e., "No reminder" as well.

The third group's data will be collected retrospectively via hospital records. The intent of the 3rd arm is to estimate the “true” baseline for the number of visits without any extra attention given by the medical staff, in order to prevent inadvertent behavior modification through perceived observation bias.

6. 2. Study Procedure

Pregnant Syrian refugee women who are in their first trimester of pregnancy will be enrolled in the study. Participants will be enrolled from the Obstetrics and Gynecology department of refugee health clinics in Istanbul. Participants will be randomized and enrolled into intervention or either of the two control arms (refer to section 6.5. Randomization Strategy for details).

For the intervention arm, participants will be given the consent form. After having consented to participate in the study, they will be given the socioeconomic and health history form. In what follows, they will receive a 30-minutes brief about the mobile app HERA and will be asked to download it. The mobile application will automatically plan out the dates of further prenatal care appointments based on the date of the last menstruation. Participants will receive reminders in the form of push notifications for prenatal checkup dates for 6 months. Reminders will be sent at the following intervals: 1) 2 weeks before, 2) 1 day before and 3) on the day of the recommended appointment. After the recommended appointment date, participants will receive push notifications asking whether or not they went to the appointment in weekly intervals for 1 month. This reminder algorithm will be used for each prenatal checkup for a total of three appointments post the baseline visit: once in second trimester and two in third trimester, using the World Health Organization and Turkish Ministry of Health prenatal checkup calendar. At the end of 6 months of follow up time, participants in the intervention arm will be contacted via phone call to ask for any remaining appointments or unanswered notifications. Completeness of 3 prenatal care appointments post the baseline visit, as recommended by WHO and implemented by Turkish MoH will be compared to the control groups.

Participants in the informed control arm will be given the consent form and will be asked for their contact information if consented. They will also be given the socioeconomic and health history form. Participants in the non-informed control group just will be given the socioeconomic and health history form. Both the informed and non-informed control group members will be

reached out at the end of the 6-month study period to be asked about the number of prenatal care appointments they attended. If unable to be reached, retrospective chart review of the participant's medical record will be attempted, in order to obtain the number of attended prenatal care appointments.

6. 2. 1. Recruitment Strategy

Participants will be enrolled from the obstetrics and gynecology department of refugee health clinics in Istanbul, Turkey with the help of a translator (Turkish to Arabic). The enrollment will take place with the help of the physician.

6. 3. Study Population

The population included in this study are pregnant Syrian refugee women between the ages of 18 to 49, who are in their first trimester of pregnancy.

6. 3. 1. Eligibility

Inclusion Criteria:

- Having the status of “Syrian under temporary protection”
- Being in the first trimester of the pregnancy
- Initial prenatal visit
- Age equal or greater than 18 years and less than or equal to 49

Exclusion Criteria:

- Having a citizenship or a status other than “Syrian under temporary protection”
- Not owning a mobile phone
- Being unable to read and write
- Not initial prenatal visit
- Having a chronic disorder or high-risk pregnancy that requires the individual to go to the hospital frequently. Frequently is defined as more than 3 visits post the baseline visit.
- While gestating, those that develop a high-risk pregnancy that requires more than 3 visits post the baseline visit.

6. 4. Sample Size Determination

The primary outcome measure for the power and size calculation is the difference in the mean number of visits among the different arms of the study. We set our target detectable difference in means to be 0.5 or more additional visits. As the maximum standard deviation is 1.5 due to the restricted range of 0 to 3 visits, our target effect size is $0.5/1.5 = 0.33$. Our calculation shows that each arm will need at least 40 patients to have a power of 90% and a two tailed significance level of 0.05. Due to the nature of refugees, we anticipate a high loss due to follow up and other reasons for dropout. Without prior information, we assume a 20% loss rate and therefore inflate the number of patients per arm by 25%. Thus, we plan to enroll 54 patients per arm for a total of 162 individuals. The statistical software G*Power Version 3.1.9.6 available from the UCLA Institute for Digital Research & Education Statistical Consulting website; [G*Power \(ucla.edu\)](http://G*Power (ucla.edu)), was used for the calculations.

6. 5. Randomization Strategy

Subjects will be selected on the following basis: randomly select a week and recruit on 6 days of that week. On 3 of the days the selection process will start in the morning, denoted as AM, (the first part of the day that is expected to see half of the patients) and on the other 3 days the selection process will start in the afternoon, denoted as PM, (the second part of the day that is expected to see half of the patients.) For each AM/PM session, the first 27 subjects giving approval to be in the study will be randomly assigned into one of the 3 arms. It is estimated that 100 to 200 women use the hospital daily. Thus, we feel that most likely the daily target intakes will be met. However, if not met by the end of the AM/PM shift, the selection process will stop. After day 6 and before any data analysis, a check will be done on the sample sizes and additional subjects may be recruited by selecting another week to perform additional recruiting.

This sampling plan requires that the number of women coming to see the medical staff be approximately the same day to day and AM to PM.

Details of the random assignment to AM/PM and to groups are attached. The assignment of treatment and control groups to 0, 1 or 2 will be done prior to the start of subject recruitment but will not be shared with the data analyst until after the analysis is complete.

7. Outcomes

Primary Outcome:

The primary outcome of this study is the number of medical visits, following the initial baseline PNC visit, over the 6-month period prior to childbirth.

Secondary analyses:

In the secondary analyses, we will further examine other risk factors, including sociodemographic and reproductive medical history, on the number of medical visits during the study period. The following additional data will be gathered:

1. Age
2. Highest level of education
3. Current employment status and profession if employed
4. Marital status
5. If married, whether the spouse is alive or deceased
6. If married, whether the spouse resides with the participant or not
7. Number of children
8. Ages of children
9. Miscarriage history, and the number and the timing of miscarriage, if any
10. Number of deceased children, if any
11. Number of times the participant gave birth to stillborn baby, if any
12. If prior pregnancies, the number of deliveries occurred at home and at a hospital
13. Type of delivery (vaginal, C-section) and the number of each type
14. Information on prenatal care appointments made during prior pregnancies, and the number of appointments attended
15. Information on medical conditions that require long-term medication use, if yes, the name of the condition and medication
16. Duration of time living in Turkey

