Participants will fill the sociodemographic and health history form. Their contact information will be gathered. Participants will be contacted at the end of 6 months and will be asked about the number of the prenatal care appointments they have attended during their pregnancy.

No Intervention: Uninformed Control No Reminder

Participants will fill the sociodemographic and health history form. No contact information will be gathered. The purpose of this arm is to estimate the “true” baseline for the number of visits without any extra attention given by the medical staff.

Outcome Measures

Primary Outcome Measure: Rate of attendance for prenatal care visits: The number of 4 mandatory prenatal care appointments that are attended are presented here.

Secondary Outcome Measure: Sociodemographic and Health information form data: Data about sociodemographic and health information of participants will be presented here.

Eligibility

Minimum Age: 18 Years

Maximum Age: 49 Years

Sex: Female

Gender Based: No

Accepts Healthy Volunteers: Yes

Criteria:

Inclusion Criteria:

- Having the status of “Syrian under temporary protection”
- Being in the first trimester of the pregnancy
- Initial prenatal visit
- Age equal or greater than 18 years and less than or equal to 49

Exclusion Criteria:

- Having a citizenship or a status other than “Syrian under temporary protection”
- Not owning a mobile phone
- Being unable to read and write
- Not initial prenatal visit
- Having a chronic disorder or high-risk pregnancy that requires the individual to go to the hospital frequently. Frequently is defined as more than 3 visits post the baseline visit.
- While gestating, those that develop a high-risk pregnancy that requires more than 3 visits post the baseline visit.

Contacts/Locations

Central Contact Person: [name]

[contact]

Email: [contact]

Study Officials: [name]

Study Principal Investigator Founder/CEO

Sociodemographic and Health History Form (will be filled with the assistance of a translator)

1. Age:
2. What is your highest level of education?
 - a. Undergraduate
 - b. High School
 - c. Middle School
 - d. Elementary school
 - e. Can read
 - f. Can not read
3. Do you currently work? If yes, what is your profession?
.....

4. Are you married?

- a. Yes
- b. No

5. Is your spouse alive?

- a. Yes
- b. No

6. Does your spouse live with you?

- a. Yes
- b. No

7. How many children do you have?

- a.
- b. Doesn't have any

8. How old are your children?

Child 1 age:

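### The primary outcome is captured by a different method in each arm of an open-label trial, and the passages on how the uninformed arm is measured contradict one another

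*Combined protocol and SAP*

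**What the plan says.** **Uninformed control arm.** SAP section 6.1 says that the third group's "data will be collected retrospectively via hospital records". SAP section 6.2 says that both control groups will be "reached out at the end of the 6-month study period to be asked about the number of prenatal care appointments they attended", and that charts are reviewed if a woman cannot be reached. The same section mentions contact details only for the informed controls; of the others it says "Participants in the non-informed control group just will be given the socioeconomic and health history form". The protocol's Arms and Interventions entry for this arm says "No contact information will be gathered".

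**Reminder arm (SAP section 6.2).** After each recommended date, "participants will receive push notifications asking whether or not they went to the appointment in weekly intervals for 1 month". Then: "At the end of 6 months of follow up time, participants in the intervention arm will be contacted via phone call", to fill in remaining appointments and unanswered prompts.

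**Informed control arm (SAP section 6.2; protocol, Arms and Interventions).** One question at 6 months. In the protocol it covers appointments over the pregnancy.

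**Fallback (SAP section 8.3).** Calls and record review, for subjects with missing data only.

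**What is counted, and over what period.** SAP section 7 and the protocol's Detailed Description agree: medical visits after baseline, in the 6 months before childbirth. Other places differ:
- SAP section 6.2 compares "Completeness of 3 prenatal care appointments post the baseline visit" over 6 months of follow-up.
- SAP section 6.4 assumes a range of 0 to 3.
- The protocol's Outcome Measures entry counts four mandatory appointments.
- SAP section 8.4 runs the final analysis 6 months after the trial starts.

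**The concern.** The primary analysis (SAP section 8.1) is a one-way ANOVA of visit counts across the three arms. It reads a difference in means as a difference in attendance. That needs a visit to have the same chance of being counted in every arm. Here a woman in the reminder arm is asked several times close to each date and then telephoned, an informed control must recall about 6 months in one answer, and an uninformed control is represented by whatever the searched charts hold. Because the trial is open-label, self-report may also be coloured by knowing the arm.

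The third arm is exposed most. Its stated purpose is to show the visit rate without extra attention from staff, and that comparison works only if its visits are counted as in the other arms. Withholding the arm codes from the data analyst (SAP section 6.5) does not equalise how the data were gathered.

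**Working it through.** **1. Can the three instructions for the uninformed arm all be followed?**

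| Place | Instruction |
|---|---|
| SAP 6.1 | Hospital records |
| SAP 6.2 | Contact and ask; charts if not reached |
| Protocol, Arms and Interventions | No contact details taken |

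No. Without contact details the women cannot be called, so the first step of SAP 6.2 fails and its fallback applies. All three routes then end at charts. As executed, the sources are: reminder arm, app answers plus call; informed controls, one recall; uninformed controls, charts.

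**2. Does SAP section 8.3 align them?** No. It acts only when data are missing, so a woman who answered keeps the source of her arm.

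**3. Three or four visits?** Entry requires the initial prenatal visit, so counting the baseline visit adds exactly 1 per woman. Counted in all arms, differences are unchanged. Counted in one arm only (for example, if informed controls answer for the whole pregnancy), it shifts that arm by 1.0 visit, twice the 0.5-visit target.

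**4. Window.** Assumptions: enrolment at week 6 to 13, 6 months = 26 weeks, delivery at week 40. Follow-up ends at 6 + 26 = week 32 to 13 + 26 = week 39, which is 40 − 32 = 8 to 40 − 39 = 1 weeks before delivery. Two of the three post-baseline visits fall in the third trimester, so late visits can be lost, but in every arm. SAP section 6.5 plans one recruitment week (6 × 27 = 162), so 6 months from enrolment and 6 months from trial start nearly coincide unless a further week is added.

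**5. Size of unequal capture.**

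The plan's own figure first: 40 per arm is reproduced by a three-group ANOVA (noncentral F) with 0.33 entered as Cohen's f (power 0.902). This point does not depend on that figure.

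Inputs from SAP section 6.4: 54 per arm, 20% loss, SD 1.5, target 0.5 visits. Analysed per arm: 54 × 0.8 = 43.2, taken as 43. Assumed, not in the documents: no true effect, mean 1.5 visits, one arm under-captured by 10% or 20%.

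- False difference d = under-capture × mean: 0.10 × 1.5 = 0.15; 0.20 × 1.5 = 0.30.
- ANOVA at SD 1.5: noncentral F on 2 and 126 df, noncentrality 43 × (2/3) × d² / 1.5². This is 0.287 and 1.147.
- ANOVA with binomial counts out of 3 (SD about 0.87): simulation.

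| Under-capture in one arm | False difference | ANOVA rejects, SD 1.5 | ANOVA rejects, binomial |
|---|---|---|---|
| 0% | 0 | 5% | 5% |
| 10% | 0.15 | 7.2% | about 12% |
| 20% | 0.30 | 14.3% | about 36% |

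Mean 1.5 is used because an SD of 1.5 is attainable for a 0-to-3 count only there. At mean 2 the maximum is √(2 × 1) = 1.414.

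**6. Which comparison is hit?** If only the uninformed arm is under-captured, a simulated reminder versus informed control test stays at about 5%. The distortion falls on the omnibus test and on contrasts with the uninformed arm.

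**The case against.** The best reply is that the contradiction is one misplaced sentence. SAP section 6.1 and the protocol agree with each other, and the fallback in SAP 6.2 leads to the same place. This stands. A reader might infer that the third arm's outcome is undefined; the documents do not support that, because it defaults to charts. The default, however, is what makes the sources differ by arm.

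A reader might also infer that the reminder effect itself is shown to be biased. It is not. Under-capture confined to the uninformed arm leaves reminder versus informed control untouched, and SAP section 8.1 also reports arm means with intervals. That contrast is biased only if app prompts plus a call capture visits differently from a single recall. This is plausible, but the documents give neither size nor direction.

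Nor is it right that no definition or window exists: SAP section 7 and the protocol's Detailed Description give one, the same for all arms. The fault is that other sections conflict with it. The range of 0 to 3 has partial support, since women whose high-risk pregnancy or chronic disorder needs more than three post-baseline visits are excluded. That does not cap extra medical visits by other women.

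Finally, a common 6-month stop loses late visits in all arms and does not by itself bias the comparison.

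**Conclusion.** The point holds in this form: the passages on the uninformed arm conflict, and the plan as it would be executed measures the primary outcome by three different methods without naming a common source. The visit definition and the window are stated once and contradicted elsewhere.

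The damage cannot be sized from the documents. Under assumed under-capture of 10% to 20% in one arm, at mean 1.5 and 43 per arm, the false difference is 30% to 60% of the 0.5-visit target (0.15/0.5 and 0.30/0.5). The nominal 5% ANOVA rejects between about 7% and 36% of the time, depending on the capture rate and the spread of the counts. The omnibus test and comparisons with the uninformed arm carry this risk; reminder versus informed control carries it only if those two arms' methods capture visits differently. This should be settled before data collection.

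**What to change.** 1. Reconcile SAP sections 6.1 and 6.2 and the protocol's arm description on how the uninformed arm is measured.
2. Set one countable-visit definition that excludes the baseline visit (medical or prenatal visits, and whether visits beyond three count) and one window for every arm. Align SAP sections 6.2, 6.4, 7 and 8.4 and the protocol's Detailed Description, arm descriptions and Outcome Measures with it.
3. Pre-specify one primary source applied identically to all three arms. Chart abstraction is the practical option, because it is already planned and the uninformed arm has no contact details. Use the same form for all 162 women, abstract without knowledge of arm where feasible, and state which facilities' records are searched.
4. Keep app and telephone self-report, with the same definition and window, as a sensitivity outcome in the reminder and informed arms, and report its agreement with charts.
5. Confirm that chart access is covered by consent or ethics approval in every arm. SAP section 6.5 says that "the first 27 subjects giving approval to be in the study will be randomly assigned into one of the 3 arms", whereas SAP 6.2 describes only the history form for uninformed women. The protocol records board approval, so this is a check and not a finding of fault.

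**Cost.** The text changes are free before data collection. Abstraction grows from the uninformed arm and unreached women to all 162. A window to childbirth would delay the last count by 1 to 8 weeks per woman under the assumptions above. The protocol's dates span 52 weeks, and week 6 to week 40 takes 34, leaving 52 − 34 = 18 weeks for recruitment.

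**Downside.** Charts miss visits outside the searched records, and the documents say nothing about completeness. Equal under-capture of 10% or 20% shrinks a true 0.5-visit effect to 0.5 × 0.90 = 0.45 or 0.5 × 0.80 = 0.40. Unequal capture could still mislead: with true means of 2.0 (reminder) and 1.5 (control), capture of 80% and 90% shows 1.60 − 1.35 = 0.25, and the reverse shows 1.80 − 1.20 = 0.60. This is the reason to keep self-report alongside.

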7.1. Populations and subgroups to be analyzed Per Protocol (PP)

All randomized study subjects not rejected over the observation period and having complete data will be the basis of the analysis. Subjects with missing data will be excluded from the analysis. This will be the primary population for the analysis.

8. Analysis

All outcomes will be presented using descriptive statistics, continuous data by the mean, standard deviation and a plot of the pdf. Binary and categorical variables will be presented in tables using counts. R version 4.0.5 will be used for all statistical analysis.

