8.1. Primary Analysis

The primary analysis will be a standard one-way fixed effect ANOVA comparing the 3 arms. The resulting ANOVA results and the arm means with 95% confidence intervals will be presented.

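### Eligibility asks only for a mobile phone, but the reminder arm needs one that can run the HERA app; women without such a phone would dilute the effect, and could bias it if failed installs count as rejections

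*Combined protocol and SAP*

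**What the plan says.** SAP 6.3.1 and the Eligibility section of the protocol list the same phone exclusion: "Not owning a mobile phone". Neither asks for a smartphone or for a device compatible with the app.

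SAP 6.1 says that the intervention group "will download and use the HERA application to receive appointment reminders through push notifications". The Reminder arm description in the protocol also delivers reminders by push notification. No other reminder channel is described.

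On timing, SAP 6.5 says that in each session "the first 27 subjects giving approval to be in the study will be randomly assigned into one of the 3 arms". SAP 6.2 then says of the intervention arm, after consent and the history form, that "they will receive a 30-minutes brief about the mobile app HERA and will be asked to download it". No device check before assignment is described.

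The only statement on phone access is in SAP 5.1, repeated in the protocol's background: "Mobile phone penetration is high among Syrian refugees in Turkey". It concerns mobile phones in general.

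SAP 7.1, headed as a per-protocol population, says: "All randomized study subjects not rejected over the observation period and having complete data will be the basis of the analysis". It does not say what counts as rejection, and it plans no analysis by assigned arm regardless of installation.

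**The concern.** The phone criterion is weaker than what the intervention needs. A woman with a basic phone passes screening and can be assigned to any arm. In the reminder arm her phone is found wanting at the download step. In either control arm nobody asks, so her counterpart is never identified.

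Two consequences are possible, depending on how the plan is applied:

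- **She is kept.** The reminder arm then includes women who cannot receive reminders, and the difference between arms shrinks.
- **She is treated as rejected.** She leaves the reminder arm while similar women stay in the controls, so the arms no longer differ only by randomisation.

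The plan does not say which applies.

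**Working it through.** **Inputs from the SAP.** Section 6.4 gives a target difference of 0.5 visits, SD 1.5, effect size 0.5/1.5 = 0.33, 90% power, two-tailed alpha 0.05, 40 per arm, 20% loss and 54 enrolled per arm. Section 8.1 gives the test: "The primary analysis will be a standard one-way fixed effect ANOVA comparing the 3 arms".

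**Assumptions, not in the documents.** The share p of women whose phone cannot run the app is taken as 5%, 10% or 20%. Reminders are assumed to have no effect in them.

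**Step 1: the plan's own figure.** Power of a three-arm one-way ANOVA comes from the noncentral F distribution with noncentrality f² × 3n. With f = 0.33 entered as the ANOVA effect size, the smallest n giving 90% is 40 per arm (power 90.2%), which matches the SAP. With f unrounded at 1/3, power at 40 per arm is 90.8% and the smallest n is 39.

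**Step 2: dilution if these women are kept.** The expected difference is 0.5 × (1 − p), f becomes (1 − p)/3, and the sample needed grows by about 1/(1 − p)².

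**Step 3: a pairwise view.** After 20% loss, 54 × 0.8 = 43.2, so 43 per arm. Power for reminder against one control comes from the noncentral t distribution with standardised difference 0.5 × (1 − p)/1.5.

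| Share p | Difference (visits) | f | ANOVA power, 40 per arm | n per arm for 90% | 1/(1 − p)² | Pairwise power, 43 per arm, SD 1.5 |
|---|---|---|---|---|---|---|
| 0 | 0.50 | 0.333 | 90.8% | 39 | 1.00 | 33% |
| 5% | 0.475 | 0.317 | 87.5% | 44 | 1.11 | 31% |
| 10% | 0.45 | 0.300 | 83.6% | 48 | 1.23 | 28% |
| 20% | 0.40 | 0.267 | 73.5% | 61 | 1.56 | 23% |

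The two power columns start far apart because the SAP's 40 per arm follows only if the standardised difference of 0.33 is entered as the ANOVA f. That is a separate matter. Both bases are shown because the loss from dilution appears on each.

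**Step 4: bias if these women are dropped from the reminder arm only.** Let g be the gap in mean visits, without reminders, between women with and without a capable phone. The reminder arm then has the capable women's mean plus the effect. A control arm has the capable women's mean minus p × g. The difference is therefore shifted by p × g. With assumed gaps of 0.25 to 1.0 visits:

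- p = 10%: 0.10 × 0.25 = 0.025 to 0.10 × 1.0 = 0.10 visits
- p = 20%: 0.20 × 0.25 = 0.05 to 0.20 × 1.0 = 0.20 visits

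These compare with a target of 0.5. The shift favours the reminder arm if women without a capable phone attend less often, and goes the other way if they attend more.

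**The case against.** **The share may be near zero.** The documents give no figure, and the source for phone access is marked confidential. The consent form is not in the text reviewed, so a device requirement stated there cannot be ruled out. This stands: the size is unknown, and at 5% the loss is about 2 to 3 percentage points of power on the two bases above. A reader might infer that the criterion is wrong at any share above zero. The documents do not support that; a negligible share would do negligible harm.

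**Dilution may be part of the effect sought.** If the aim is the effect of offering the app to any woman with a phone, those who cannot install it belong in the comparison and cost power without causing bias. The objective does speak of pregnant Syrian refugee women generally. But the hypotheses in SAP 5.3 concern sending reminders, and a per-protocol population does not estimate the effect of an offer.

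**Exclusion is not certain.** A reader might infer that the sentence "Subjects with missing data will be excluded from the analysis" in SAP 7.1 removes these women. It would not do so by itself. The six-month call in SAP 6.2 reaches a basic phone, and SAP 8.3 adds calls and hospital record review, so their outcome can still be obtained. The only open route to exclusion is the undefined word 'rejected'. This part of the objection stands, and the bias is therefore conditional.

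**No intervention at all is too strong.** Every woman in the reminder arm is to receive the 30-minute briefing before the download. Zero effect is therefore an assumption, and some benefit would soften the dilution.

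**Conclusion.** The mismatch is real and follows from the text: the plan admits women who may be unable to receive the reminders under test, and finds this out only after assignment and only in one arm. Dilution is the direct consequence if they are analysed. Bias follows only if failed installs are treated as rejections.

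For shares of 5% to 20% and no effect in these women, ANOVA power at 40 per arm drops by 3.3 to 17.3 percentage points. Pairwise power at 43 per arm with SD 1.5 drops by about 3 to 10 points. The conditional bias is 0.025 to 0.20 visits for shares of 10% to 20% and the assumed gaps. The shares, the zero effect and the gaps are all assumptions.

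A reader might also infer that dropping these women would leave a better-educated reminder arm. Nothing in the documents links phone type to education, and women unable to read and write are excluded from every arm. That inference is not part of this point.

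This is a modest weakness that is worth correcting because the correction is cheap, not one that invalidates the design.

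**What to change.** In SAP 6.3.1 and in the protocol's Eligibility section, change the phone exclusion to: not owning a phone able to install the HERA app and receive push notifications. Check this before assignment, with the same question or test for every woman whichever arm she will enter. For the third arm this requires that women are met in person before assignment, as SAP 6.2 and 6.5 describe.

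In SAP 7.1, state that a woman who still fails to install the app after assignment is analysed in her assigned arm, and that a failed install is not a ground for rejection. Reporting the proportion of the reminder arm that installed the app would show how much dilution remains.

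The cost is one eligibility line in each document, one screening step and one sentence in 7.1. Recruitment will be slightly slower and the population slightly narrower, so the results will apply to owners of app-capable phones. If the change is made, the dilution term from device type is zero and this point requires no change to the sample-size calculation.
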